Has the participant selection process overprotected potential subjects who are considered vulnerable so that they are denied opportunities to participate in research?

Yes No

4. Number of participants to be included and/or enrolled in this entire study, across all study locations: 1,920 consent cover letters sent; up to 20,000 EHR records

At Utah prior to October 2019: 960 consent cover letters sent; up to 20,000 EHR records

5. Characteristics of Participants/Inclusion Criteria:

Adapted Criteria for Genetic Testing for Inherited Cancer Susceptibilities
First Degree Relative or Second Degree Relative diagnosed with the following regardless of age: Ovarian Cancer, Pancreas Cancer
First Degree Relative or Second Degree Relative diagnosed with the following <50 years of age: Breast Cancer, Colorectal Cancer, Endometrial Cancer
Three or more relatives on the same side of the family diagnosed with the following clusters of cancer regardless of age:
Breast Cancer, Ovarian Cancer, Pancreas Cancer, Prostate Cancer
Colorectal Cancer, Endometrial Cancer, Ovarian Cancer, Pancreas Cancer, urinary tract, brain, small intestine
Melanoma, Pancreas Cancer
Ashkenazi Jewish ancestry and family history of Breast Cancer, Ovarian Cancer, Pancreas Cancer, Prostate Cancer

Inclusion Criteria:

Criteria will be simplified to focus on first- and second-degree relatives, specific cancer type, number of family members, and age at diagnosis (See Table)

The algorithms to stratify patients' risk for this study will be based on National Comprehensive Cancer Network (NCCN) criteria for testing for genes in the homologous DNA repair pathway associated with breast, ovarian, prostate, and pancreas cancer and Lynch syndrome, and international consensus recommendations for genetic testing for hereditary melanoma.

Participants will be eligible to participate if they speak English.

Future possible amendment will to be include Spanish speaking patients.

6. Participant Exclusion Criteria:

Exclusion Criteria:

We will exclude patients who have a prior cancer diagnosis, other than non-melanoma skin cancer, and/or prior genetic counseling or testing related to hereditary cancer.

We will also exclude patients who do not have access to internet and therefore unable to access the patient portal.

7. Is a substantial percentage of the participant population anticipated to be non-English speaking?

Yes No

IRB_00123563

Created: 6/5/2019 3:01 PM

PI: [name]

Submitted: 3/5/2019

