Patients meeting National Comprehensive Cancer Network guidelines for referral for genetic services will be identified using the screening tool developed and implemented in the EPIC EHR (Study Aim 1). The primary care providers (PCPs) of eligible patients will be notified of their patient's eligibility one week prior to patients being notified of the recommendation for genetic services. Patients will then be referred to participate in standard of care genetic services, with the clinical procedures depending on the study arm to which the clinic was randomized: enhanced standard of care or patient-directed standard of care.

Patients meeting criteria will be notified of the recommendation through the patient portal (i.e. MyChart). Those who do not have MyChart will be notified by mail. Those notifications will be followed by standard scheduling procedures. Patients who do not have MyChart will be asked to sign up for MyChart when they are contacted. Those who were not actively using MyChart will be provided with a refresher on the use of MyChart since this project focuses on using this tool to deliver genetic services more effectively.

Patients who do not have access to the internet or are unwilling or able to use MyChart will be directed to in person genetic counseling services. A waiver of consent will be requested to track the individuals who are not able to participate through MyChart, but they will not be asked to complete study questionnaires.

Study Arms – Clinic Randomized

Enhanced Standard of Care

This arm is referred to as enhanced since clinical decision support (CDS) tools are used to identify patients meeting guidelines rather than relying solely on provider identification of patients. Patients in this arm will have an in-person or telephone pre-test genetic counseling visit. Pre-test counseling includes review of the family history, risk assessment, discussion of the purpose of genetic testing and possible outcomes, implications for insurance coverage, costs, and assessment of psychosocial needs.

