iii. After each returned questionnaire, participants will be compensated via the patient portal with a thank you message and a \$10 e-gift card. This totals \$20 dispersed if both questionnaires are returned.

iv. For any participants who would like to complete questionnaires by telephone, a genetic counseling assistant or research coordinator will administer the questionnaire. Calls will be digitally recorded to allow for analysis of comprehension. Each questionnaire will take about 15 minutes to complete. Participants may also complete the questionnaires by mail if they choose.

4. Study staff will track the EHR of participants who were identified by the CDS algorithms. Any screenings, care or health procedures related to genetic services will be recorded in the research record to determine if an impact is made because of participation in genetic services. This is estimated to be up to 20,000 individual records in the EHR.
5. Data analysis for outcome data will occur after patient enrollment is complete. Patients who return questionnaires will be compared to similar cohorts that were not directly involved with research questionnaires.

More specific details of data analysis are outlined in the statistical methods section.

7. Are all procedures for research purposes only (non-standard or non-standard of care procedures)?

Yes No

If no, list the procedures that are performed for research purposes only (non-standard or non-standard of care procedures):

Questionnaire #1: estimated 4-8 weeks from last genetic services contact (4 weeks for those who decide to test and 8 weeks for those who decide not to test)

Questionnaire #2: estimated 12-months from last genetic services contact

Data Analysis of genetic services impact and outcomes

8. Is there a safety monitoring plan for this study?

Yes No

9. Provide a summary of the statistical methods, data analysis, or data interpretation planned for this study. Factors for determining the proposed sample size (e.g., power) should be stated.

Research Aims Analysis for this specific IRB:

Aim 2 Analysis.

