Aim 2 analyses will address the dimensions of Reach, Effectiveness, Adoption, and Implementation from our conceptual framework. For Effectiveness, we will be testing for equivalence between study arms in uptake of genetic testing. We will check randomization by comparing demographic characteristics between patients in the two arms. Any characteristic(s) that are significantly different will be controlled for in the multivariable analysis. We will examine descriptive statistics, and will use Fisher's Exact test with a two-sided 0.05 significance level for univariate comparison of proportions to examine the association between study arm and uptake of genetic testing. We will next build multilevel multivariable logistic regression models to examine the effect of study arm on the outcome controlling for clinic-level (clinic type, patient volume, patient composition, number of providers), provider-level (specialty, years in practice, gender), and patient-level (e.g., sociodemographic, clinical) variables. We will examine the intra-class correlation (ICC) by clinic and provider. If a significant ICC is observed, the regression models will be extended to include random effects for clinic or provider, and fit using software for generalized mixed models. Covariates will be included in models if significant in unadjusted analyses. For Reach, using the multivariable regression models with interaction terms, we will examine whether the effects of study arm on uptake of genetic testing is modified by race/ethnicity or rurality. For Adoption, we will examine the proportions of providers and patients who access educational resources and with referrals, and whether this differs by population subgroup. For Implementation, we will assess responses to patient portal messages and completion of study workflows. Statistical significance will be assessed as $p < 0.05$; SAS 9.4 and/or Stata 15.1 will be used for analysis.

Aim 2 Sample Size

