Sample size for Aim 2 was calculated using PASS 15 based on an equivalence test for the difference of two proportions in a cluster-randomized design. Sample sizes of 480 in the patient-directed arm and 480 in enhanced standard of care arm, which were obtained by sampling 32 clusters (clinics) with 15 participants each and 16 clusters (clinics) with 30 participants each, respectively, achieve 80% power to detect equivalence. The margin of equivalence, given in terms of the difference between proportions, extends from -0.10 to 0.10. The calculations assume Likelihood Score Tests (Farrington & Manning) were used with an ICC of 0.05, and a significance level of 0.05. We believe that this is likely an overestimate of ICC based on our prior work. This sample size is sufficient for a multilevel multivariable regression analysis and achieves >95% power to detect a small effect size (0.02) attributable to 1 independent variable using an F-Test with an alpha of 0.05, adjusted for an additional 20 independent variables. To examine effect modification, sample size is calculated based on logistic regression of a binary response variable (Y) on a binary independent variable (X) and a binary confounder variable (Z). A sample size of 1,710 observations achieves 80% power at a 0.05 significance level to detect the X-Z interaction odds ratio of 1.5, using a two-sided Wald test. We will therefore enroll 1,920 patients in the Aim 2 trial to allow for about 10% attrition.

Aim 3 Analysis

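### The Aim 2 uptake denominator is undefined, and the no-internet exclusion would act after the clinic's arm is fixed, on the channel that delivers only the patient-directed service

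*Combined protocol and SAP*

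**What the plan says.** Three places in the protocol form deal with patients who cannot or will not use the portal.

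- **Section 3, item 6 (exclusion criteria):** "We will also exclude patients who do not have access to internet and therefore unable to access the patient portal". No arm is named, and unwillingness is not mentioned.
- **Section 4, item 6, Patient Screening:** patients without internet are not excluded. They and those who "are unwilling or able to use MyChart will be directed to in person genetic counseling services" (the sentence evidently means unable) are tracked under a waiver of consent and receive no questionnaires. Also: "Patients who do not have MyChart will be asked to sign up for MyChart when they are contacted".
- **Section 4, item 6, Research Procedures, item 1:** access to MyChart is a condition for the research procedures. Yet item 3.iv offers telephone completion and adds: "Participants may also complete the questionnaires by mail if they choose".

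Arms are assigned by clinic. In the enhanced arm, "Patients in this arm will have an in-person or telephone pre-test genetic counseling visit". In the patient-directed arm the pre-test service comes through the portal.

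On analysis (section 4, item 9): "For Effectiveness, we will be testing for equivalence between study arms in uptake of genetic testing". "The margin of equivalence, given in terms of the difference between proportions, extends from -0.10 to 0.10". The Aim 2 text names no uptake denominator, no intention-to-treat set, no rule for patients sent to in-person counselling, and no sensitivity analysis.

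**The concern.** Whether a patient has internet access, and whether the patient will use MyChart, comes to light when staff make contact. By then the clinic's arm is fixed, and the form describes no blinding of those staff. The two facts also mean different things in the two arms. A patient-directed patient who will not use the portal has declined the pre-test service being tested. An enhanced-arm patient with the same attitude can still attend in person or by telephone.

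If such patients are dropped from the uptake comparison, the exclusion follows randomisation and is tied to the intervention. If they are sent to in-person counselling and counted, part of the patient-directed arm receives the comparator's type of service. The three sections permit either, and each gives a different difference to set against the margin. The equivalence conclusion could therefore depend on a rule that is not written down. A lesser cost is that exclusion narrows the population in a trial that plans comparisons by rurality and race/ethnicity.

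**Working it through.** **Inputs from the form (section 4, item 9, Aim 2 Sample Size).** Margin ±0.10. There are 480 patients per arm: 32 clinics of 15 (patient-directed) and 16 clinics of 30 (enhanced). The calculation is made "with an ICC of 0.05, and a significance level of 0.05", for 80% power. The form gives neither an expected uptake nor the share of patients without a usable portal.

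**The plan's own figure.** Design effect = 1 + (m − 1) × 0.05, which is 1.70 for m = 15 and 2.45 for m = 30. Effective sizes are 480/1.70 = 282.4 and 480/2.45 = 195.9. With two one-sided tests at a true difference of zero, 80% power is met at these uptakes:

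- 0.05 per side: 0.156 (Farrington–Manning variance) to 0.161 (unpooled);
- 0.025 per side: 0.118 to 0.126.

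At 30% uptake and 0.05 per side, power is about 52%. Without an uptake assumption the 80% cannot be confirmed or refuted. I use 30% uptake for illustration and 16% as a lower value.

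**Set-up (all values assumed).**

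- q: share without a usable portal, the same in both arms
- p, e: uptake among portal users in the patient-directed and enhanced arms
- r: uptake of non-portal patients in the enhanced arm, relative to e
- v: uptake of non-portal patients in the patient-directed arm

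Differences are patient-directed minus enhanced:

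- Everyone counted by clinic arm: D_all = (1 − q)p + qv − [(1 − q)e + qre]
- Non-portal patients excluded in **both** arms: D_ex = p − e
- Shift from exclusion: D_ex − D_all = q[p − v − e(1 − r)]

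v = 0 means these patients stay in the portal pathway and none is tested. v = re means they are sent to in-person counselling and behave like their enhanced-arm counterparts; then D_all = (1 − q)(p − e).

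**Size of the shift (p = e, v = 0), in points.** With p = e and v = 0 the shift is q × p × r.

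| | q = 5% | q = 10% | q = 20% |
|---|---|---|---|
| p = e = 0.30, r = 1 | 1.5 | 3.0 | 6.0 |
| p = e = 0.30, r = 0.5 | 0.75 | 1.5 | 3.0 |
| p = e = 0.16, r = 1 | 0.8 | 1.6 | 3.2 |

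**Can it change the conclusion?** Take q = 10% and r = 1.

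| | Counted, v = 0 | Excluded in both arms | Counted, v = re |
|---|---|---|---|
| p = 0.30, e = 0.38 | 0.27 − 0.38 = −11.0 | −8.0 | 0.9 × (−8.0) = −7.2 |
| p = 0.40, e = 0.30 | 0.36 − 0.30 = +6.0 | +10.0 | 0.9 × 10.0 = +9.0 |

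In the first row a true difference outside the margin moves inside it. In the second row the difference moves away from zero. With r = 0 and v = 0, D_all = (1 − q)(p − e), so exclusion again moves the difference away from zero.

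**The case against.** **The exclusion may concern the questionnaires only.** Section 3, item 4 counts participants as consent cover letters sent, plus EHR records. Research Procedures item 4 tracks patients identified by the algorithms in the EHR. The continuing review submitted in January 2024 counts enrolment by questionnaire completion. On that reading non-portal patients miss the questionnaires but still count for uptake. This is possible, but it is not stated. The Aim 2 sample size speaks of enrolling 1,920 patients, the same number as the cover letters, so the two populations are not cleanly separated. The form's front page points to a full protocol published elsewhere, which I have not seen and which may define the set.

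**Portal status is partly known beforehand.** A reader might infer that it is all learned at contact. It is not: MyChart account status decides between portal and mail notification. Only internet access and willingness come later.

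**The rule names no arm.** A reader might infer that only the patient-directed arm loses patients. The screening text precedes the arm descriptions, and both arms use the portal for notification and questionnaires. Loss from one arm alone would need unequal application, which is plausible but not in the documents. Equal application still shifts the difference, as shown above.

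**The direction is not fixed.** A reader might infer that the rule must favour equivalence. It does so only if patient-directed uptake would otherwise be lower. No section predicts that, and the Background presents patient-directed features as a way to increase access.

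**In-person fallback can be part of the model.** Patient-directed patients may ask for a genetic counsellor appointment at any time. Counting fallback uptake in that arm is then a choice of estimand rather than an error. This stands, and the fix has to state it.

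**Conclusion.** The concern holds in a limited form. The three sections do not agree on who is excluded, re-routed or gated, and the Aim 2 analysis does not say who counts. If the exclusion is applied to uptake, it is a post-randomisation exclusion linked to the patient-directed service. It shifts the difference in favour of that arm when non-portal patients would have used the enhanced service and would not have been tested through the portal, even if it is applied in both arms.

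The size cannot be computed from the documents. Under the stated assumptions it is about 1.5 to 6 points at 30% uptake, against a 10-point margin, and about half that at 16% uptake or r = 0.5. These figures take v = 0, a portal pathway with no effective fallback. With r = 1 the shift is q(p − v), so it shrinks as re-routed patients take up testing and vanishes at v = p. The documents do not establish a bias of known direction or amount. They leave open a choice that can decide whether the result falls inside the margin.

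**What to change.** 1. Reconcile section 3, item 6 with the Patient Screening text and Research Procedures item 1 in section 4, and state which condition governs eligibility, service and questionnaires. How these patients are served is for the investigators to settle.
2. In the Aim 2 analysis, define the denominator as all eligible patients identified by the decision-support algorithms, analysed in their clinic's randomised arm, with uptake from the EHR. Internet access or portal willingness learned at contact should remove nobody from it.
3. Pre-specify a sensitivity analysis in patients with an active portal account on the identification date, taken from the EHR in both arms before contact.
4. If re-routing stays, state that the clinic-arm comparison is of the portal model with in-person fallback. That analysis does not remove dilution from re-routing, so report the number and uptake of re-routed patients by arm.

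The cost is analysis wording and one extra EHR field. Tracking of the identified patients is already planned, and portal message history is already on the list of data to be collected. The downside is that patient-directed uptake may look somewhat lower.

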Research Aims to be studied in this protocol:

Aim 2) Compare uptake of genetic testing for patient-directed standard of care vs. enhanced standard of care genetic services delivery models for 1,920 unaffected primary care patients. We will utilize a randomized trial design with clinic-level randomization to compare two standard of care models: a *patient-directed standard of care* model and an *enhanced* model. In the *patient-directed* model those identified by the clinical decision support (CDS) infrastructure as meeting testing criteria will be informed of their cancer risks, provided with educational resources, and offered the option to select genetic testing through a patient portal. This online portal will be overseen by HCI genetic counselors. The *enhanced standard of care* model in which primary care providers and patients are notified through CDS when criteria are met (the *enhancement* of standard of care) and of the availability of standard of care genetic services. We will compare uptake of genetic testing by model and by race/ethnicity and rurality.

Aim 3) Compare adherence to recommendations and other patient responses for the genetic services delivery models. We will compare the effects of the genetic services delivery models on adherence to management recommendations at 12 months after return of results, or last genetic services contact. We will assess cognitive (i.e., recall, comprehension, uncertainty, risk perceptions) and affective (i.e., test-related distress, positive reactions, decision regret) responses at 4 weeks, and communication (i.e., family, provider) interactions at 4 weeks and 12 months after last genetic services contact. We will also examine differences in effects by race/ethnicity and rurality.

7. Is this a multi-site study, where more than one site needs IRB approval?

Yes No

8. Background and Introduction:

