Research Procedures

1. A research coordinator or genetic counseling assistant will determine who is eligible to participate in the research procedures based on participation in genetic services and access to MyChart, the patient portal. A waiver of recruitment is being requested for this authorization. Up to 20,000 unique electronic health records may be accessed to determine inclusion in this study, and basic health outcomes tracked for comparison.
2. Consent cover letter will be sent via patient portal to offer participation in this research study, with a link to an online questionnaire. The consent cover letter will be sent to patients approximately 4 weeks after genetic test results are returned for those who decide to test and about 8 weeks after participation in pre-test genetic counseling services for those who decide not to test.

If no response is received to the first message, after 1 week another message in the patient portal will be sent. If still no response up to 3 phone calls will be made.

3. Online questionnaires will utilize REDCap, which has a HIPAA-compliant interface. Estimated 960 patients will be offered participation through University of Utah Health; 1,960 patients over both participating sites.

i. **Questionnaire #1:** At about **4 weeks after return of results for those who decide to test** (8 weeks after pre-test genetic counseling), we will assess cognitive (i.e., recall, comprehension, uncertainty, risk perceptions), affective (i.e., test-related distress, positive reactions, decision regret), communication (i.e., family, provider) responses, experience with genetic counseling, and sociodemographic characteristics including numeracy for those who decide to test. For those who do not decide to test, we will assess experience with genetic counseling, reason for not testing, decision regret, risk perceptions, and sociodemographic characteristics including numeracy.

ii. **Questionnaire #2:** At about **12 months**, we will ask about discussion of their test results with their PCP, family members, or others, and self-reported use of cancer screenings for those who decide to test. We will also utilize EHR data to examine adherence to recommendations. For those who decide not to receive genetic testing, we will assess the self-reported use of cancer screenings, whether genetic testing was pursued at another time or through another source, communication with family members and whether other relatives had testing.

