Q2 Invitation-No testing.docx(0.01)	0.01	7/14/2020 3:54 PM	7/14/2020 3:54 PM	8/11/2020 3:10 PM
Q2 Invitation-Testing.docx(0.01)	0.01	7/14/2020 3:54 PM	7/14/2020 3:54 PM	8/11/2020 3:10 PM
Q1 Mail Coverletter_Testing_NYU.docx(0.01)	0.01	7/15/2020 2:44 PM	7/15/2020 2:44 PM	8/11/2020 3:10 PM
Q1 Mail Coverletter_No testing_NYU.docx(0.01)	0.01	7/15/2020 2:44 PM	7/15/2020 2:44 PM	8/11/2020 3:10 PM
Q2 Mail Coverletter_Testing_NYU.docx(0.01)	0.01	7/15/2020 2:45 PM	7/15/2020 2:45 PM	8/11/2020 3:10 PM
Q2 Mail Coverletter_No testing_NYU.docx(0.01)	0.01	7/15/2020 2:45 PM	7/15/2020 2:45 PM	8/11/2020 3:10 PM
Q1 mail coverletter-No testing_Utah.docx(0.01)	0.01	7/15/2020 2:45 PM	7/15/2020 2:45 PM	8/11/2020 3:10 PM
Q1 mail coverletter-Testing_Utah.docx(0.01)	0.01	7/15/2020 2:45 PM	7/15/2020 2:45 PM	8/11/2020 3:10 PM
Q2 mail coverletter-Testing_Utah.docx(0.01)	0.01	7/15/2020 2:45 PM	7/15/2020 2:45 PM	8/11/2020 3:10 PM
Q2 mail coverletter-No Testing_Utah.docx(0.01)	0.01	7/15/2020 2:58 PM	7/15/2020 2:58 PM	8/11/2020 3:10 PM
Q1 mail coverletter-No testing_Utah_Spa_Final.docx(0.01)	0.01	9/1/2020 3:25 PM	9/1/2020 3:25 PM	9/15/2020 10:58 AM

Name	Version	Date Created	Date Modified	Date Approved
Q2 Mail Coverletter_No testing_NYU_Spa_Final.docx(0.01)	0.01	9/1/2020 3:25 PM	9/1/2020 3:25 PM	9/15/2020 10:58 AM
Q2 Invitation-Testing_Spa_Final.docx(0.01)	0.01	9/1/2020 3:25 PM	9/1/2020 3:25 PM	9/15/2020 10:58 AM
Q1 invitation-Testing_Spa_Final.docx(0.01)	0.01	9/1/2020 3:25 PM	9/1/2020 3:25 PM	9/15/2020 10:58 AM
Q1 Mail Coverletter_No testing_NYU_Spa_Final.docx(0.01)	0.01	9/1/2020 3:25 PM	9/1/2020 3:25 PM	9/15/2020 10:58 AM
Q2 mail coverletter-Testing_Utah_Spa_Final.docx(0.01)	0.01	9/1/2020 3:25 PM	9/1/2020 3:25 PM	9/15/2020 10:58 AM
Q1 invitation-No testing_Spa_Final.docx(0.01)	0.01	9/1/2020 3:25 PM	9/1/2020 3:25 PM	9/15/2020 10:58 AM
Q1 Mail Coverletter_Testing_NYU_Spa_Final.docx(0.01)	0.01	9/1/2020 3:25 PM	9/1/2020 3:25 PM	9/15/2020 10:58 AM
Q2 mail coverletter-No Testing_Utah_Spa_Final.docx(0.01)	0.01	9/1/2020 3:25 PM	9/1/2020 3:25 PM	9/15/2020 10:58 AM
Q1 mail coverletter-Testing_Utah_Spa_Final.docx(0.01)	0.01	9/1/2020 3:25 PM	9/1/2020 3:25 PM	9/15/2020 10:58 AM
Q2 Invitation-No testing_Spa_Final.docx(0.01)	0.01	9/1/2020 3:25 PM	9/1/2020 3:25 PM	9/15/2020 10:58 AM
Q2 Mail Coverletter_Testing_NYU_Spa_Final.docx(0.01)	0.01	9/1/2020 3:25 PM	9/1/2020 3:25 PM	9/15/2020 10:58 AM

Updated Recruitment Materials, Advertisements, etc.:

Name Version Date Created Date Modified Date Approved

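### MyChart access is a condition for the Aim 3 questionnaires, so service users with internet who are outside the portal drop out of the questionnaire-based outcomes after clinic randomization, and the protocol's sections disagree on who is surveyed

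*Combined protocol and SAP*

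**What the plan says.** All references are to the combined protocol and SAP.

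- **Patient Screening (4. Study Information, item 6).** Patients without internet, or "unwilling or able to use MyChart will be directed to in person genetic counseling services" (I read the second adjective as unable). A waiver is requested "to track the individuals who are not able to participate through MyChart, but they will not be asked to complete study questionnaires".
- **Research Procedures 1.** Staff decide who is "eligible to participate in the research procedures based on participation in genetic services and access to MyChart, the patient portal".
- **Item 4b (recruitment).** The consent cover letter and questionnaires go to patients who complete genetic counseling, with no portal condition.
- **3. Participants, item 6.** Patients without internet access are excluded. Unwillingness or inability to use MyChart is not listed.
- **Consent Process, items 2 and 3.** The cover letter goes to all who receive genetic services, but through the portal, and consent is taken there.
- **Other channels.** On notification of the recommendation: "Those who do not have MyChart will be notified by mail". Research Procedures 3.iv offers telephone completion and adds: "Participants may also complete the questionnaires by mail if they choose". The continuing review submitted in March 2021 lists approved mail cover letters for both sites. Under Research Procedures 3.iii, payment is an e-gift card sent through the portal.
- **Aim 3.** After listing the cognitive, affective and communication outcomes, the aim states: "We will also examine differences in effects by race/ethnicity and rurality".

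**The concern.** The enhanced service does not need the portal. Counseling is in person or by telephone, results are given by phone or in person, and the results letter can be posted. A patient can complete that whole pathway and still be left out of the survey because of the channel used to invite people, although the study already runs mail and telephone modes.

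Two things are at stake. First, recall, distress, regret, family and provider communication and self-reported screening would describe portal users only. So would their comparisons by race/ethnicity and rurality, in a trial whose background makes unequal access a main reason for the work. Second, the filter acts after clinics are randomized. In patient-directed clinics it removes patients who did not take up the portal model and were sent to in-person counseling. If the proportion removed differs between arms, the questionnaire contrast is no longer protected by randomization.

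**Working it through.** **1. Who is surveyed, section by section**

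| Group | Exclusion criteria | Item 4b | Patient Screening and Research Procedures 1 |
|---|---|---|---|
| MyChart users | included | surveyed | surveyed |
| Internet, but unwilling or unable to use MyChart | included | surveyed if counseled | served and tracked, not surveyed |
| No internet | excluded | not addressed | served and tracked, not surveyed |

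The middle row is the problem: no exclusion criterion covers these patients, yet they are barred. The last row is a declared population limit, although Patient Screening still serves and tracks those patients. The survey population is not defined until these sections agree.

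**2. The plan's own figure**

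The Aim 3 Sample Size section gives N = 1,100, effect size 0.02, 2 tested variables, 20 covariates, alpha 0.05 and power above 90%. For a noncentral F test, the denominator df is 1,100 - 2 - 20 - 1 = 1,077, and the noncentrality is 0.02 × 1,100 = 22. Power is 99.1%, so the stated figure holds as a lower bound (clustering ignored). If 5%, 10%, 20%, 30% or 40% of the 1,100 were lost (assumed shares), power would be 98.8%, 98.4%, 97.1%, 94.9% or 91.1%. At the planned size, then, the harm is selection and generalizability rather than main-effect power.

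**3. Completers forgone**

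The continuing review submitted in January 2023 reports about 450 patients (Utah) and 480 (NYU) invited to Questionnaire #1, and 307 enrolled in the sense of completing research questionnaires.

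- Response: 307 / (450 + 480) = 307 / 930 = 33%.
- Let s be the share of service users barred by the MyChart condition (not given; 5-30% assumed). If all 930 were portal users, extra invitees = 930 × s / (1 - s). Multiply by 0.33 for extra completers, assuming the same response.

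| s | Extra invitees | Extra completers | Relative to 307 |
|---|---|---|---|
| 5% | 49 | 16 | +5% |
| 15% | 164 | 54 | +18% |
| 30% | 399 | 132 | +43% |

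**4. Effect on estimates**

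- *Description of all service users.* If barred patients differ by 20 points on a binary response (assumed), the portal-only figure is off by s × 0.20, which is 1 to 6 points for s of 5-30%.
- *Arm contrast.* If barred patients differ by d SD from portal users, equally in both arms, the shift is (difference in barred share between arms) × d. With assumed values: 0.05 × 0.3 = 0.015 SD, up to 0.20 × 0.5 = 0.10 SD. With equal shares it is zero.
- *Yardstick.* An f-squared of 0.02 for one balanced two-level factor is 2 × √0.02 = 0.28 SD. The plan attributes 0.02 to two variables, so this gives scale only.

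**The case against.** The strongest reply is that this is a chosen scope. Patients without internet are a stated exclusion, and Patient Screening explains that the project is about delivering services through MyChart. That stands for the no-internet group. It does not cover patients with internet, and it does not explain withholding a survey from people counseled in person.

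The case for unequal selection by arm is also weaker than it looks. Portal notification, the request to sign up and the refresher all sit under screening common to both arms, so portal status partly surfaces before the arms diverge, and sign-up help shrinks the barred group. A reader might infer that the arm contrast is biased. The documents show only that it could be, since they give no barred share by arm.

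Inviting these patients has an analytic cost. In patient-directed clinics they receive in-person counseling, which resembles the comparator. Analyzing them by clinic arm may pull the contrast toward equivalence, in a trial that hypothesizes equivalence for uptake and adherence. That is why a portal-users-only analysis should sit alongside.

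The waiver requests plan a comparison of questionnaire participants with non-participants. It can describe selection on recorded characteristics but cannot supply missing responses.

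Finally, the rule may have been superseded. Two questionnaire-outreach amendments were submitted in July and October 2020, and the mail cover letters were approved in August 2020. Only the amendment titles are visible, and nothing shows that the condition was lifted or kept.

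**Conclusion.** The point holds for the questionnaire-based Aim 3 outcomes (cognitive, affective, communication, self-reported screening) and their race/ethnicity and rurality comparisons. Service users with internet but outside MyChart are barred without an exclusion criterion that covers them, and the sections contradict one another. It is worth correcting because the remedy is cheap.

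Its size cannot be established. The 16-132 extra completers rest on an assumed barred share and equal response. The 0.015-0.10 SD shift also needs an assumed difference in barred share between arms, and its upper end needs both extremes together.

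Two stronger readings are not supported. A reader might infer that all of Aim 3, or every subgroup comparison, rests on portal users. It does not: adherence also draws on EHR data, barred patients are tracked under the waiver, and Aim 2 uptake needs no questionnaire. A reader might also blame this rule for the shortfall to 335 completers (237 + 98) in the continuing review submitted in January 2024, against 1,100 planned. The documents do not allow that attribution. Even the 30% case gives only 307 + 132 = 439 on the January 2023 count.

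**What to change.** 1. In Patient Screening and Research Procedures 1, replace the MyChart condition with an invitation of these service users by mailed consent cover letter and telephone, at the same time points, using the existing mail and telephone modes.
2. Bring the related text into line: the exclusion criteria (state whether patients without internet stay excluded), item 4b, Research Procedures 3.iii (payment through the portal only) and Consent Process items 2 and 3 (consent through the portal only).
3. Record portal status and questionnaire mode for every respondent.
4. Analyze by the clinic's randomized arm, with a portal-users-only analysis alongside.
5. If a later outreach amendment already invites these patients, correct the text to say so. If re-invitation is no longer possible (the January 2024 review reports Utah closed to enrollment and NYU finishing Questionnaire #2), correct the text, report the number barred by arm, and limit the questionnaire conclusions to portal users.

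Cost: a short IRB amendment moving these patients from waiver-only tracking to cover-letter consent, postage, a non-portal payment route, and calls by existing coordinators. The price in the data is more mixed response modes and the possible pull toward equivalence that step 4 is meant to expose.
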